PILOT PHASE II MULTICENTER STUDY OF THE PI3K INHIBITOR COPANLISIB IN COMBINATION WITH A KETOGENIC DIET IN THE TREATMENT OF PATIENTS WITH RELAPSED OR REFRACTORY FOLLICULAR LYMPHOMA OR ENDOMETRIAL CANCER

NCT04750941

Protocol date: 9/23/2024

PROTOCOL SYNOPSIS

Study Design: This is a multi-institution, open label, pilot phase II study of the PI3K inhibitor copanlisib in combination with a ketogenic diet in the treatment of patients with one of the following malignancies: (a) relapsed or refractory (R/R) follicular lymphoma (FL), (b) R/R endometrial cancer (EC) with a documented activating mutation in PIK3CA or loss of PTEN. The FL arm will enroll 23 subjects and the EC arm will enroll 19 subjects. The study will be stopped if the safety trigger is activated at the pre-specified times of interim safety analysis upon enrollment of 12 and 24 patients.

The two arms will enroll patients in parallel and independently. Safety analysis will be done by pooling patients from the two arms together. Efficacy analysis will be conducted independently within each arm.

Objectives: Primary Objectives

- Determine the objective response rate (ORR) (complete response [CR] + partial response [PR]) in FL.
- Determine the ORR in EC.

Secondary Objectives:

- Determine the CR and PR rates in FL upon completion of the study protocol.
- Determine the CR and PR rates in EC upon completion of the study protocol.
- Determine the ORR in FL and EC at the Simon stage I analysis
- Determine patient compliance with the ketogenic diet.

Exploratory Objectives:

- Determine the PD markers including *blood* levels of insulin, c-Peptide, BHB (beta-hydroxybutyrate), triglyceride, and glucose, and urine ketones.
- Determine the PD markers including levels of pINSR, INSR, pAKT, AKT, pS6, S6, Ki-67, TUNEL, caspase, and actin in paired pre- and post-treatment *tumor* tissues in patients who consented for the optional post-treatment biopsy of the tumors (blood and bone marrow are acceptable if they are known to be involved by lymphoma).
- Explore the correlation of disease response and the PD markers described above.
- Explore the correlation of disease response and gene alternations in tumor tissues.
- Explore the correlation of insulin response and gene alternations in normal buccal fibroblasts.
- Determine the change in body weight and body mass index (BMI) over time.
- Determine the change in computed tomography-based body composition metrics including

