(RECIST) guideline. CT or PET/CT scan will be performed after every two 28-day cycles of. After cycle 4, if the patient has achieved CR, scans will be done every 3 cycles.

Data analysis:

All patients receiving at least one dose of copanlisib will be evaluable for toxicity and all patients completing at least one 28-day cycle of therapy (copanlisib plus ketogenic diet) will be evaluable for response and time-to-endpoint analyses.

Response will be estimated with exact 95% confidence intervals (CIs). We will estimate overall survival, progression-free survival, and duration of response using the Kaplan-Meier method. Group comparisons, between groups associated with different biomarkers described below, will be made using a two-sided log-rank test, and the estimated hazard ratios and 95% CIs will be calculated using Cox regression. Overall survival will be assessed post hoc in the trial patients. In the exploratory correlative biomarker analyses, any patients with assessable biological samples (blood, tumor etc) will be included. An association between disease outcome (complete response, partial response, stable disease, progression of disease, duration of response, and progression-free survival) and changes from baseline in biomarker concentrations as a function of treatment over time will be assessed. Because of sample size considerations, we will base group comparisons for these analyses on two-sample t test. We will do correlative studies including all enrolled patients that have adequate biological samples available for analysis. We plan to assess changes over time and estimate odds ratios using mixed-effects logistic regression models or a linear model if the sample sizes for comparison are too small. We will summarize continuous variables as means and SDs, and categorical variables as counts with percentages. We will not do multiple testing adjustments. All the analyses will be done with SAS version 9.4.

Study Rationale

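### The biomarker log-rank tests have no grouping rule, so continuous markers would have to be cut for PFS and duration of response; a continuous Cox term avoids the loss

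*Combined protocol and SAP*

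**What the plan says.** The Data analysis part of the Protocol Synopsis estimates overall survival, PFS and duration of response by Kaplan-Meier. On biomarkers it continues: "Group comparisons, between groups associated with different biomarkers described below, will be made using a two-sided log-rank test". The effect measure for these comparisons is given in the same sentence: "the estimated hazard ratios and 95% CIs will be calculated using Cox regression". It does not say whether the marker enters the Cox model as a group or as a continuous term.

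The same paragraph then says that an association between disease outcome and "changes from baseline in biomarker concentrations as a function of treatment over time will be assessed". Its list of outcomes includes PFS and duration of response as well as response category. For these analyses it adds "we will base group comparisons for these analyses on two-sample t test", and later plans to "estimate odds ratios using mixed-effects logistic regression models or a linear model if the sample sizes for comparison are too small". It states that no adjustment for multiplicity will be made.

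The Exploratory Objectives name the markers. In blood and urine they are "levels of insulin, c-Peptide, BHB (beta-hydroxybutyrate), triglyceride, and glucose, and urine ketones". In paired tumor tissue they are "levels of pINSR, INSR, pAKT, AKT, pS6, S6, Ki-67, TUNEL, caspase, and actin". A separate objective reads "Explore the correlation of disease response and gene alternations in tumor tissues"; those markers form groups without a cut.

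**The concern.** A log-rank test compares groups. A concentration, or a change in one, has no groups until somebody picks a threshold, and the public text gives no threshold, quantile or other rule.

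Two things could go wrong. A fixed split discards information in arms that are already small, so real associations could be missed. A split chosen after looking at the curves inflates false positives, and no multiplicity adjustment limits the damage. Hazard ratios from different cut-points would also be hard to compare with later studies.

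A smaller point concerns natural groups, such as gene altered or not. If one group holds only a few patients, the large-sample log-rank p-value tends to be too small.

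The trial's rationale is that the diet suppresses insulin feedback. Relating insulin and ketone changes to PFS is therefore one of the more informative exploratory readouts.

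**Working it through.** **Plan's own figures.** The documents give no power, event count or cut-point for the biomarker tests, so there is nothing to reproduce directly. The arm sizes used below, 23 (FL) and 19 (EC), come from the two Simon designs. An exact two-stage binomial sum, P(X1 > r1 and X1 + X2 ≥ r), gives:
- FL: attained type I error 0.043 and power 0.801 (stated 5% and 80%).
- EC: attained type I error 0.099 and power 0.821 (stated 10% and 81%).

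The sizes are sound for their ORR purpose.

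**Assumptions not in the documents.** Marker distribution, position of the split, censoring fraction, effect size and size of the natural groups. Ranges are shown where they matter.

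**Step 1: information kept by a split.** For a normal marker cut at quantile q, the share kept is φ(z_q)² / [q(1 − q)].
- Median: 0.3989² / 0.25 = 0.637, a loss of 36%. In effect 23 × 0.637 = 14.6 patients and 19 × 0.637 = 12.1.
- 40/60 cut: loss 38%. 25/75: loss 46%. 20/80: loss 51%.
- Uniform marker cut at the median: share kept 0.75, loss 25%.

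**Step 2: power.** Simulation with a standard normal marker, exponential times, hazard ratio 2 per SD and a score test at two-sided 5% (critical value 3.841), 20,000 runs per setting. Ranges cover independent repeats.

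| Censoring | n = 23, continuous v median split | n = 19, continuous v median split |
|---|---|---|
| None | 78-79% v 57-58% | 69% v 47-49% |
| About 30-34% | 65-66% v 43-46% | 56% v 36-39% |
| About 51% | 54% v 37% | 45% v 30% |

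The gap is 15 to 22 points throughout.

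**Step 3: false positives at nominal 5%, no true effect.**
- Continuous Cox term: about 6%.
- Fixed median cut: 6-7%.
- Best of five quantile cuts: 21-23%.
- Best cut between the 20th and 80th percentiles: 29-32%.

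**Step 4: small natural groups.** Rejection rate of the large-sample log-rank test at nominal 5%, 100,000 runs, group sizes assumed:

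| Censoring | 3 v 20 | 3 v 16 | 5 v 18 |
|---|---|---|---|
| None | 9.0% | 8.6% | 7.3% |
| About 30% | 8.0% | 7.8% | 6.7% |
| About 50% | 7.2% | 7.1% | 6.2% |

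**Step 5: actual numbers.** 23 and 19 are upper limits. Only patients with adequate samples count, and the post-treatment tumor biopsy is optional. Duration of response exists only in responders: at the design alternatives that is 0.67 × 23 ≈ 15 (FL) and 0.30 × 19 ≈ 6 (EC). Power would be lower than in Step 2.

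**The case against.** The strongest reply is that the plan never says continuous markers will be dichotomised. A reader might infer that it does, but the text speaks only of groups associated with biomarkers. Some of those are gene alterations, which lose nothing, and the Cox model in the same sentence could take a continuous term. This stands: the split is an inference from the choice of test. What remains is that the grouping is undefined while the markers described next are concentrations.

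A second reply is that the t tests and mixed models already keep concentrations continuous. That is right for response categories. It does not cover PFS or duration of response, because a t test does not handle censored times; the log-rank and Cox sentence is the only time-to-event method given.

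Third, the public text is largely a synopsis. It refers to Sections 5.6 and 6.6 and Appendix 5, none of which is reproduced, so a grouping rule could sit elsewhere. The absence can be claimed only for the text available.

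Fourth, a reader might take the loss of about a third, or the 30% false-positive rate, as properties of this trial. Neither is. The first depends on the marker's distribution and the cut. The second describes a search over cuts that nobody has planned, although nothing in the available text rules it out. Likewise, groups of 3 to 5 patients have no prevalence figure behind them, and the excess over 5% is small.

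Finally, these are exploratory analyses, openly unadjusted. That limits the importance of the point but does not define the comparison.

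**Conclusion.** The point holds as a minor one. For PFS and duration of response, the only stated biomarker method needs groups, most named markers are continuous, and the available text gives no rule for forming the groups.

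If a roughly normal marker is cut at the median, the loss is about 36% of the information (25% for a uniform marker, 51% for a 20/80 cut of a normal one). At an assumed hazard ratio of 2 per SD, this costs roughly 20 points of power with no censoring or about one-third censoring, at sample sizes that are themselves ceilings. A data-chosen cut could give about 30% false positives per marker; a fixed median cut would not. In assumed natural groups of 3 to 5 patients, the large-sample log-rank test rejects about 7-8% of the time at moderate censoring.

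A reader might infer that the trial's main result is at risk. The documents do not support that: the ORR tests and the stopping rules do not use these comparisons. Nor are the gene-alteration groups weakened by splitting, or the t tests and mixed models affected.

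**What to change.** In the Data analysis text:

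1. For continuous markers and time-to-event outcomes, enter the marker as a continuous term in the Cox model already planned. Use log2 of the baseline level, or log2 of the on-treatment to baseline ratio; a raw change can be zero or negative and cannot be logged. State a rule for zero or undetectable values. Where a log scale does not suit, use per-SD scaling or, for semi-quantitative markers, ordinal coding.
2. For on-treatment changes, start follow-up at a landmark at the time of measurement, because the value is not known at time zero.
3. Show median-split curves for display only.
4. Keep the log-rank test for natural groups, such as gene altered v not altered, with permutation p-values.

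The cost is analysis-plan wording and some care over the landmark and undetectable values; no extra patients, samples or visits are needed. The downsides are that the continuous term assumes a roughly log-linear effect, and that a landmark drops patients whose event comes before it.

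### No classification time, landmark or time-dependent method is given for survival comparisons by on-treatment biomarker change, so they are open to immortal-time bias

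*Combined protocol and SAP*

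**What the plan says.** All the relevant text is in the Data analysis section of the Protocol Synopsis, read with the Objectives.

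- Endpoints: "We will estimate overall survival, progression-free survival, and duration of response using the Kaplan-Meier method".
- Comparison: "Group comparisons, between groups associated with different biomarkers described below, will be made using a two-sided log-rank test". Cox regression is to supply hazard ratios with their intervals.
- Biomarker variable that follows: association of disease outcome, with PFS and duration of response in the list, with biomarker change: "changes from baseline in biomarker concentrations as a function of treatment over time will be assessed".
- Next sentence: "Because of sample size considerations, we will base group comparisons for these analyses on two-sample t test". Mixed-effects logistic or linear models are named for changes over time.
- Population: "all patients completing at least one 28-day cycle of therapy (copanlisib plus ketogenic diet) will be evaluable for response and time-to-endpoint analyses". Separately, the sample-size section replaces patients who do not complete two cycles.

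The exploratory objectives name both kinds of marker. Some are measured repeatedly on treatment ("levels of insulin, c-Peptide, BHB (beta-hydroxybutyrate), triglyceride, and glucose, and urine ketones"). Others are fixed at baseline ("Explore the correlation of disease response and gene alternations in tumor tissues"). The text does not say which kind forms the log-rank groups, what cut-off applies, or by what date a patient is classified.

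**The concern.** Treatment continues until progression, unless toxicity, withdrawal or the investigator's judgment ends it sooner. A patient who stays progression-free longer therefore has more on-treatment samples. Glucose, one of the listed markers, is checked on every infusion day, three times per cycle. Someone who progresses early has few chances to be seen to change. If patients are sorted by whether a change was ever seen, and survival is counted from the start of treatment, the event-free waiting time is credited to the changed group. An ordinary log-rank or Cox analysis then favours that group even when marker and outcome are unrelated.

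The direction matters. The Study Rationale proposes that the diet mitigates copanlisib-induced hyperinsulinemia and so improves response and survival. The artefact points the same way and could be read as confirmation of the mechanism. No multiplicity adjustment is planned for these comparisons.

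**Working it through.** The plan gives no event count, hazard ratio, power or alpha for these comparisons, so there is no figure of its own to reproduce.

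**1. Mechanism.** Let p be the chance per cycle of first showing the change, independent of outcome. The chance of being classed as changed within k cycles is 1 − (1 − p)^k. At p = 0.20, a patient who progresses after 3 cycles has 1 − 0.8³ = 0.49, and one followed for 12 cycles has 1 − 0.8¹² = 0.93. Group membership depends on survival although the marker does not.

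**2. Inputs from the documents.** 23 FL and 19 EC patients; reference median PFS 11.2 months in FL (Study Rationale); entry to time-to-event analysis after one 28-day cycle.

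**3. Assumptions.** Exponential PFS after that first cycle; EC median 4 or 6 months (the documents give none); 24 months of follow-up; sampling once per cycle; mean time to change 2, 4 or 8 months; two-sided 5%; no true association. A cycle is 28/30.4375 = 0.92 months, so these means correspond to 1 − exp(−0.92/mean) = 37%, 21% and 11% per cycle. Each setting had 4,000 replicates; those with fewer than two patients in a group were dropped.

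**4. False-positive rate of the log-rank test, for mean time to change of 2 / 4 / 8 months**

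| How groups are formed | FL, 11.2 mo | EC, 4 mo | EC, 6 mo |
|---|---|---|---|
| Change at any time | 0.97 / 0.94 / 0.83 | 0.82 / 0.78 / 0.60 | 0.89 / 0.85 / 0.71 |
| Change by end of cycle 4, no landmark | 0.19 / 0.10 / 0.06 | 0.33 / 0.15 / 0.07 | 0.26 / 0.12 / 0.07 |
| Change by end of cycle 2, no landmark | 0.06 / 0.06 / 0.06 | 0.08 / 0.07 / 0.06 | 0.09 / 0.06 / 0.07 |
| Change fixed at end of cycle 1 | 0.06 / 0.07 / 0.08 | 0.07 / 0.07 / 0.09 | 0.07 / 0.08 / 0.09 |
| Landmark at end of cycle 2 | 0.06 / 0.06 / 0.07 | 0.07 / 0.08 / 0.09 | 0.07 / 0.07 / 0.08 |

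In the two window rows, patients who progress before showing a change count as unchanged.

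Dropped replicates matter most in the first FL cell, where 2,433 of 4,000 were usable. Counting every dropped one as non-significant still leaves 0.972 × 2,433/4,000 = 0.59.

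**5. Sensitivity.** A separate run with the same one-cycle entry rule and an assumed 5-month EC median gave about 57–94% (FL) and 51–86% (EC) for change at any time, 6–12% and 7–22% for a cycle-4 window, 6–8% for a cycle-2 window, and 6–8% for the cycle-2 landmark. For FL without the entry rule, with 18 months of follow-up and change counted over at most 12 cycles, the any-time rule gave 45%, 78% and 91% at p = 10%, 20% and 30%.

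**6. Residual level.** The 6–9% under the landmark is the small-sample level of the asymptotic log-rank test at these sizes, not immortal time.

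**7. Patients lost to a cycle-2 landmark (2 × 0.92 = 1.84 months).**
- FL from treatment start: 1 − 2^(−1.84/11.2) = 0.108, times 23 = 2.5.
- FL given one completed cycle: 1 − 2^(−0.92/11.2) = 0.055, times 23 = 1.3.
- EC given one completed cycle: 1 − 2^(−0.92/4) = 0.147, times 19 = 2.8; with a 6-month median, 0.101 × 19 = 1.9.

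**The case against.** The strongest reply is that the plan nowhere says the log-rank groups are formed by on-treatment change. It names a t test for the change-from-baseline analyses, which fits comparing biomarker change between responders and non-responders. Gene alterations are fixed at baseline and fit the log-rank sentence without any immortal time. The pharmacodynamic objective itself speaks of disease response, not PFS. Diet-driven markers should move during the ketogenic run-in, before copanlisib starts, so months of waiting for a change are implausible for ketones. The one-cycle evaluability rule gives every analysed patient the same guaranteed time. The work is exploratory, and the text supplied refers to protocol sections that are not in it.

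Much of this stands. A reader might infer that the plan commits to a biased analysis, or that any comparison without a landmark is biased. The documents support neither: they contain no rule based on change at any time, and classification by cycle 1 or 2 shows almost no excess even without a landmark.

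The reply does not close the gap, however. The biomarker variable described below the log-rank sentence is change over time, and PFS and duration of response are named among its outcomes. A t test cannot handle censored times, so log-rank and Cox are the only methods offered for those outcomes. The text permits the harmless and the badly biased analysis equally. The run-in argument covers ketones better than insulin, C-peptide or glucose, which also respond to copanlisib.

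**Conclusion.** The point holds conditionally. The plan relates on-treatment change to censored outcomes without saying when patients are classified and without a landmark or time-dependent method, and its log-rank and t-test sentences do not fit together. If groups use change at any time on treatment, false-positive rates are roughly 50 to 95% at 10 to 30% change per cycle (45 to 97% across all settings tried). A cycle-4 window gives about 6 to 20%, reaching 33% only with the fastest change and the shortest assumed EC median. For classification by cycle 1 or 2 the excess is negligible. These sizes rest on the assumed change rates, follow-up, EC medians and exponential PFS; the documents supply only the FL median, the sample sizes and the entry rule.

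Baseline markers are not affected. The primary ORR analyses, the two-stage decisions and the safety rules are untouched. This should be corrected before the biomarker analyses are run, but it does not threaten the trial's main conclusion.

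**What to change.** Amend the Data analysis section as follows.

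1. List which biomarkers are baseline and which are on-treatment. Keep the ordinary log-rank and Cox analysis for the baseline ones.
2. For on-treatment markers, classify by change up to the end of cycle 2, the first response evaluation, with the cut-off stated in advance. Start the PFS or OS clock there among patients still event-free. For duration of response, start at the later of response and landmark.
3. Alternatively, enter the marker as a time-dependent covariate in the Cox model, which keeps all evaluable patients.
4. Limit the t test to comparing biomarker change between response categories.

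The cost is wording, plus the few patients with an event before the landmark: at most about 2 to 3 of 23 in FL at the reference median, and nearer 1 given the one-cycle rule. In EC it is about 2 to 3 of 19 under the same rule and the assumed 4- to 6-month medians. The two-cycle replacement rule would reduce these further. A landmark does not remove the separate selection created by the one-cycle evaluability and two-cycle replacement rules; that needs its own correction.

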Dose Modification of copanlisib is described in Section 6.6.

Duration of Treatment:

Patients will be treated until one of the following events: disease progression, unacceptable adverse event(s), withdrawal of consent, general or specific changes in the patient's condition that render the patient unacceptable for further treatment in the judgment of the investigator.

Sample Size and Statistical Consideration:

The study will enroll 42 patients. The two arms will enroll patients in parallel and independently. Safety analysis will be done by pooling patients from the two arms together. Efficacy analysis will be conducted independently within each of the two arms (lymphoma, solid tumor).

Patients who do not complete the planned cycle 2 cycles of treatment, which is required for the first evaluation of response, will be replaced.

(a) The lymphoma arm will enroll 23 patients with FL.

- Simon's two-stage design (Simon, 1989) will be used. The null hypothesis that the true ORR rate is 41% will be tested against a one-sided alternative. In the first stage, 13 patients will be accrued. If there are 5 or fewer ORRs (**To be assessed after completing 4 cycles of the treatment**) in these 13 patients, the study will be stopped for futility. Otherwise, 10 additional patients will be accrued for a total of 23. The null hypothesis will be rejected if 14 or more ORRs are observed in 23 patients. This design yields a type I error rate of 5% and power of 80% when the true ORR rate is 67%. Assuming that the CR rate is 0.09 (2 out 23), with 23 subjects we will have 80% power to claim that the true CR is at least 30%.
- The reference range of ORR in FL is 40% (n = 16. Dreyling et al, Ann Oncol. 2017) to

59% (n = 104. Dreyling et al, J Clin Oncol. 2017).

• The reference CR rate is 14% (n = 104. Dreyling et al, J Clin Oncol. 2017).

(b) The solid tumor arm will enroll 19 patients with EC.

Simon's two-stage design (Simon, 1989) will be used. The null hypothesis that the true ORR rate is 0.10 will be tested against a one-sided alternative. In the first stage, 11 patients will be accrued. If there are 1 or fewer ORRs (To be assessed after completing 4 cycles of treatment) in these 11 patients, the study will be stopped for futility. Otherwise, if >=2/11 responses are observed, then 8 additional patients will be accrued for a total of 19. The null hypothesis will be rejected if 4 or more ORRs are observed in

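### The correlative analyses take patients from both diseases without naming a disease stratum or covariate, so a marker that differs by disease can appear linked to response

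*Combined protocol and SAP*

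**What the plan says.** The Data analysis section of the Protocol Synopsis defines the correlative population twice: "In the exploratory correlative biomarker analyses, any patients with assessable biological samples (blood, tumor etc) will be included", and later "We will do correlative studies including all enrolled patients that have adequate biological samples available for analysis". Neither sentence mentions the arm.

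The methods named are:
- Disease outcome against marker change: "changes from baseline in biomarker concentrations as a function of treatment over time will be assessed", with "Because of sample size considerations, we will base group comparisons for these analyses on two-sample t test".
- Time-to-event outcomes: "Group comparisons, between groups associated with different biomarkers described below, will be made using a two-sided log-rank test", with hazard ratios from Cox regression.
- Repeated measures: "We plan to assess changes over time and estimate odds ratios using mixed-effects logistic regression models or a linear model" when samples are small. Covariates are not listed.

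No disease stratum or covariate is named for any of these, and multiplicity adjustment is ruled out. Study Design and Sample Size and Statistical Consideration assign within-arm analysis to efficacy and pooling to safety. Neither mentions the correlative work.

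Three other places matter. The EC design states "The null hypothesis that the true ORR rate is 0.10 will be tested against a one-sided alternative", while the FL null is 41%; the alternatives are 30% and 67%. Under Efficacy Outcome, FL response is judged by Lugano and EC by RECIST. Under Inclusion Criteria, every EC patient must have a PI3K-pathway alteration, whereas sequencing results do not determine FL eligibility. Correlating response with tumour gene alterations is a listed exploratory objective.

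**The concern.** Confounding by disease needs two links: disease with response, and disease with the marker. The plan's own response rates supply the first. For PI3K-pathway genotype, the eligibility criteria supply the second. If FL and EC enter one unadjusted comparison, responders are mostly FL and non-responders more often EC, so a marker that merely labels the disease looks like a predictor.

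For genotype the false message would be that pathway alteration goes with non-response, in a trial of a PI3K inhibitor. Exploratory findings of this kind tend to shape the choice of markers for the next study.

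**Working it through.** **Inputs from the documents.** 23 FL and 19 EC patients; response rates 41%/10% (null) and 67%/30% (alternative); the Simon stopping rules. **Assumed.** Two-sided 5% level; normal markers; no marker-response link inside either disease; the size of the disease gap in the marker; the number of FL carriers. The plan names no test for genotype against response; Fisher's exact test is used here.

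**1. The plan's own figures.** The plan gives no operating characteristics for the correlative analyses, so the Simon designs were checked as the source of the response rates. Exact two-stage binomial:
- FL (13 patients, stop at 5 or fewer; 23 in total, reject at 14 or more): type I error 0.043, power 0.801. Stated: 5% and 80%.
- EC (11 patients, stop at 1 or fewer; 19 in total, reject at 4 or more): type I error 0.099, power 0.821. Stated: 10% and 81%.

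Both agree with the plan to within rounding and discreteness.

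**2. Disease mix by response.** FL share of responders = 23·pF / (23·pF + 19·pE); for non-responders, replace p by 1 − p.
- Null: 9.43 / (9.43 + 1.90) = 83% of responders; 13.57 / (13.57 + 17.10) = 44% of non-responders. Difference 0.39.
- Alternative: 15.41 / (15.41 + 5.70) = 73%; 7.59 / (7.59 + 13.30) = 36%. Difference 0.37.

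A marker unrelated to response within disease therefore shows a spurious responder-minus-non-responder difference of about 0.39 or 0.37 times its FL-EC gap.

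**3. Genotype.** All 19 EC patients and f of 23 FL patients are carriers. Response rate in carriers = (f·pF + 19·pE) / (f + 19); in non-carriers, pF. Exact enumeration of Fisher's test at full accrual:

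| f | Rates FL/EC | Carriers vs non-carriers | Spurious odds ratio | False p<0.05 |
|---|---|---|---|---|
| 0 | 41/10 | 10% vs 41% | 0.16 | 56% |
| 3 | 41/10 | 14% vs 41% | 0.24 | 44% |
| 6 | 41/10 | 17% vs 41% | 0.30 | 34% |
| 0 | 67/30 | 30% vs 67% | 0.21 | 59% |
| 3 | 67/30 | 35% vs 67% | 0.27 | 47% |
| 6 | 67/30 | 39% vs 67% | 0.31 | 32% |

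**4. Concentrations.** Simulation, 20,000 trials per setting at full accrual. The pooled t test compares responders with non-responders; the adjusted model is marker change on response plus arm.

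| FL-EC gap in change | Pooled, 41/10 | Pooled, 67/30 | With arm |
|---|---|---|---|
| 0 | 5% | 5% | 5% |
| 0.25 SD | 6% | 6% | 5% |
| 0.5 SD | 8% | 9% | 5% |
| 1 SD | 16% | 19% | 5% |
| 2 SD | 36% | 40% | 5% |

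**5. Effect of the Simon stops.** At the null rates FL stops at 13 with probability P(X ≤ 5) = 0.54 and EC at 11 with P(X ≤ 1) = 0.70, so both arms fill in only 0.455 × 0.303 = 14% of trials. With the stops applied, the 1 SD figures become 11% (41/10) and 18% (67/30), and the 0.5 SD figures about 7% and 9%.

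No calculation was made for log-rank or Cox. The documents give no EC progression-free survival figure to base one on.

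**The case against.** **The text never states a pooled test.** The quoted sentences say who is included. Where the plan means pooling, for safety, it says so. The outcomes being correlated are efficacy outcomes, so the within-arm rule could be read to cover them, and the mixed or linear models leave room for an arm term. This stands: a reader might infer that pooling is a stated fact, and the documents do not support that. It does not remove the point, because no sentence extends the within-arm rule to the correlative work and the named tests carry no arm term.

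**Not every marker that differs by disease will appear linked to response.** A reader might infer that it would. At an assumed 1 SD gap, more than 80% of trials at the design rates show no significant association, and at 0.5 SD more than 90%. The bias is present in expectation; a false finding is a possibility, not a certainty.

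**Concentrations are analysed as change from baseline.** A fixed FL-EC difference in level cancels, so only a disease difference in change matters, and the documents give no figure for one. Genotype has no such protection.

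**Full accrual and full sampling overstate the size.** This stands in part. The stops lower the null-rate figure, and post-treatment biopsy is optional: if half the patients have samples (assumed), the 1 SD rates with the stops fall to about 8% (41/10) and 11% (67/30). The genotype figures would also fall with fewer patients; that was not computed.

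**The objectives are exploratory.** True, and this limits the consequence. No primary or secondary conclusion, stopping rule or sample size depends on them.

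**Conclusion.** The point holds in a limited form: arm handling is unspecified in the correlative analyses, and the methods followed as written would confound marker-response associations with disease.

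The exposure is largest for PI3K-pathway genotype. That result treats the alteration as a pathway-level composite, which eligibility guarantees in EC; a single gene carried by only some EC patients would give a weaker false signal. It also rests on an assumed 0 to 6 FL carriers and on Fisher's test. For concentrations the inflation is moderate at a 1 SD difference in change and small at 0.5 SD or below. It disappears if disease does not affect the change, or if the arms are in fact analysed separately.

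This goes beyond a request for detail, because the confounder is built into the plan's own response rates and eligibility criteria and a better specification is readily available.

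**What to change.** In the Data analysis section, state that analyses relating biomarkers to disease outcome are done within each arm. Where arms are combined, include arm as a covariate in the logistic, linear and mixed models (in place of the plain t test), and use log-rank and Cox analyses stratified by arm for time-to-event outcomes.

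Add that the composite PI3K-pathway alteration cannot be related to response within EC, where every patient has it. Any information on that question comes from FL alone, and there is none if no FL patient is a carrier.

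The cost is wording, one degree of freedom in combined models, and less precise estimates within each arm. No new patients, samples or data are needed.
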